2.1. Efficacy

Primary efficacy endpoint:

- Change in systolic 24-h ambulatory BP at 6 months post-RDN-procedure from pre-procedure (including 1. Pre-treatment value (**P**) = average of the pre-procedure visit (week -1) value and screening visit (week -4) value, 2. Baseline value (**B**) = pre-procedure visit

(week -1) value only) compared *between the 2 groups* (RDN-Treatment group vs. Sham group).

Secondary efficacy endpoints:

The secondary efficacy parameters of the study are:

- Change in systolic 24-h ambulatory BP at 3 and 12 months post-procedure from pre-procedure (including P and B) compared between the 2 groups (RDN-Treatment group vs. Sham group).
- Change in diastolic 24-h ambulatory BP at 3, 6 and 12 months post-procedure from pre-procedure (including P and B) compared between the 2 groups (RDN-Treatment group vs. Sham group).
- Change in office systolic and diastolic BP at 3, 6 and 12 months post-procedure from pre-procedure (including P and B) compared between the 2 groups (RDN-Treatment group vs. Sham group).
- Change in home systolic and diastolic BP at 3, 6 and 12 months post-procedure from pre-procedure (including B only) compared between the 2 groups (RDN-Treatment group vs. Sham group).
- Responder rate in BP (systolic office BP ≥ 10 mmHg, or 24-h systolic ambulatory BP ≥ 5 mmHg) at 3, 6, and 12 months post-procedure from pre-procedure (including P and B) compared between the 2 groups (RDN-Treatment group vs. Sham group).
- Change in serum creatinine, cystatin C at all time points from pre-procedure (pre-procedure visit (week -1) value and screening visit (week -4)) compared between the 2 groups (RDN-Treatment group vs. Sham group).
- Change in eGFR (calculated based on CKD-epi formula) derived from serum creatinine at all time points from pre-procedure (pre-procedure visit (week -1) value and screening visit (week -4)) compared between the 2 groups (RDN-Treatment group vs. Sham group). [1]
- Change in eGFR derived from cystatin C at all time points from pre-procedure (pre-procedure visit (week -1) value and screening visit (week -4)) compared between the 2 groups (RDN-Treatment group vs. Sham group). [2, 3]
- Change in eGFR derived from creatinine/Cystatin-C formula at all time points from pre-procedure (pre-procedure visit (week -1) value and screening visit (week -4)) compared between the 2 groups (RDN-Treatment group vs. Sham group) [3]

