2.4. Analyses

Statistical analyses will be based on the basis of international guidelines (CPMP/ICH/363/96:E9). Due to the early stop of the study, only an exploratory and descriptive analysis takes place. Statistical methods used to compare groups for primary and secondary outcomes:

Efficacy: Change of systolic 24-h ambulatory BP at 6 months post-procedure (primary efficacy endpoint) compared between the RDN and sham group will be analyzed in a linear mixed model including the covariates that were significantly different between the groups at baseline. All secondary (see 1.1.2) and observational endpoints (1.1.3 and 1.1.4) are analyzed also via a modelling approach adjusting for potential imbalances in baseline characteristics. The type I error for the analysis of the primary endpoint is set at 5% (two-sided), all analyses of secondary endpoints have an exploratory character avoiding multiplicity issues in this trial.

In addition, a win ratio analysis will be conducted, with the criteria 24h ambulatory systolic BP change > 5 mmHg, office systolic BP change > 10 mmHg, and decrease of medication as defined by following 3 parameters (number of antihypertensive drugs, drug burden index and antihypertensive load index).

Analysis will be performed for the following populations:

1. Primary analysis is based on *the intention-to-treat* (ITT) population consisting of all randomized study subjects that are all either RDN treated or sham treated.
2. A secondary analysis will be done with a *modified ITT* population (mITT) in which participants with adherence violations will be excluded (sensitivity analyses).
3. A secondary analysis will be done with the *per protocol population* (PPP) in which study subjects with predefined protocol deviations (defined prior to unblinding of the data) are excluded.
4. A secondary analysis will be done with the modified *per protocol population* (mPPP) in which study subjects of the PPP with adherence violation are excluded.
5. A secondary analysis will be done with the safety population (SAF) in which all study subjects signing informed consent are included.

6. A secondary analysis will be done with those patients that are investigated by the Erlanger and Nürnberger center (CRC staff), with a total of N=20 randomized patients (Bavarian cohort)

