2.9. General Analysis

2.9.1. General Methodology

Descriptive statistics will be displayed for all documented and derived variables. For continuous variables, number of observations, number of missing values, mean, standard deviation, minimum, median and maximum will be calculated. For categorical variables, number of patients, absolute and relative frequencies will be calculated.

In this parallel, controlled study, data analysis will be performed using unadjusted analysis, i.e. simple paired and unpaired t-test under the assumption of a normal distribution for the difference of interest.

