2.9.4.1. Primary efficacy variable

Primary variable is the change in systolic 24-h ambulatory BP at 6 months post-procedure compared between the 2 groups.

Hence, (e.g.) the following null hypotheses H_0 , will be tested against their alternative hypotheses H_1 using unpaired t-test:

H_0 : There is no significant difference in systolic 24-h ambulatory BP at 6 months post-renal denervation compared between the 2 groups. (RDN group vs. sham group)

H_1 : There is a significant difference in systolic 24-h ambulatory BP at 6 months post-renal denervation compared between the 2 groups (RDN group vs. sham group).

The overall significance level of the trial is defined as $\alpha = 0.05$ (two-sided).

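### H0 and H1 for the primary analysis are worded on 24-h systolic BP at 6 months, not on the declared endpoint (change from pre-procedure), so the variable in the unadjusted t-test is ambiguous

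*SAP*

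**What the plan says.** SAP 1.1.1 and 2.1 give the primary endpoint as "Change in systolic 24-h ambulatory BP at 6 months post-RDN-procedure from pre-procedure", compared between the RDN and sham groups. Two pre-procedure references are listed: P, the average of weeks -4 and -1, and B, week -1 only. Section 2.4 also speaks of change, and 2.9.4.1 opens with "Primary variable is the change in systolic 24-h ambulatory BP at 6 months post-procedure compared between the 2 groups".

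Section 2.9.4.1 then moves, with 'Hence' and '(e.g.)', to hypotheses that it says "will be tested against their alternative hypotheses H_1 using unpaired t-test". H0 is "There is no significant difference in systolic 24-h ambulatory BP at 6 months post-renal denervation compared between the 2 groups" and H1 is "There is a significant difference in systolic 24-h ambulatory BP at 6 months post-renal denervation compared between the 2 groups". The same section sets a two-sided level of 0.05.

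Two other sections bear on the test. Section 2.9.1 prescribes "simple paired and unpaired t-test under the assumption of a normal distribution for the difference of interest" and does not say which difference is meant. Section 2.4 says the change in the primary endpoint "will be analyzed in a linear mixed model including the covariates that were significantly different between the groups at baseline", also at a two-sided 5% level, and describes the whole analysis as exploratory and descriptive because of the early stop.

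**The concern.** The hypotheses and the endpoint definition name different variables: attained BP at 6 months in one, change from pre-procedure in the other. In a model adjusted for the pre-procedure value this would not matter. In an unadjusted t-test it does, because the two variables give different test statistics and p-values from the same patients. An analyst who follows the hypotheses literally and one who follows the endpoint definition could report different primary p-values, and each could cite 2.9.4.1.

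There is also a defect of form. H0 and H1 assert the absence or presence of a 'significant' difference. Significance is a property of a sample result, whereas a hypothesis should state a population mean difference.

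**Working it through.** **Inputs.** From the SAP: 1:1 randomisation (1.2), an unadjusted unpaired t-test (2.9.1, 2.9.4.1) and a two-sided 5% level (2.4, 2.9.4.1). The target of 80 patients was not reached (1.2), and the final randomised number is not given. The SAP states no effect size, SD, power or pre/post correlation, so there is no figure of its own to reproduce. Assumptions: equal SD of 12 mmHg at both times, pre/post correlation r of 0.3–0.7, a true difference of 5 or 6 mmHg, and 15–40 patients per arm.

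**1. Expected effect.** Randomisation makes the expected pre-procedure difference zero, so attained BP and change have the same expected between-group difference. In simulation with a true difference of 5 mmHg, both averaged about -5.0 mmHg.

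**2. Precision.** Variance of change / variance of attained = 2(1-r), which is 1.40, 1.00 and 0.60 at r = 0.3, 0.5 and 0.7. Which test is more powerful therefore depends on r.

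**3. Agreement of the two tests.** With equal variances, the correlation between the two test statistics is (1-r)/√(2(1-r)) = √((1-r)/2):
- r = 0.3: √0.35 = 0.59
- r = 0.5: √0.25 = 0.50
- r = 0.7: √0.15 = 0.39

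Simulated unpaired t-tests (20,000 trials per setting, 5 mmHg, SD 12) gave:

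| n per arm | r | significant, attained | significant, change | exactly one significant |
|---|---|---|---|---|
| 20 | 0.3 | 25.8% | 19.6% | 23.5% |
| 20 | 0.5 | 25.0% | 24.9% | 25.8% |
| 20 | 0.7 | 24.8% | 37.6% | 34.7% |
| 30 | 0.3 | 36.1% | 27.1% | 27.7% |
| 30 | 0.5 | 35.4% | 35.3% | 31.0% |
| 30 | 0.7 | 35.0% | 53.2% | 39.9% |
| 40 | 0.3 | 45.6% | 34.5% | 30.2% |
| 40 | 0.5 | 45.5% | 45.5% | 33.1% |
| 40 | 0.7 | 45.8% | 66.7% | 39.9% |

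At 6 mmHg with 15, 20 and 40 per arm (40,000 trials per setting), exactly one test was significant in 23.7%–39.5% of trials, and in 31% at 20 per arm with r = 0.5.

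**4. False positives if either test may count.** With no effect and the correlations in step 3, the bivariate-normal probability that at least one |Z| exceeds 1.96 is 8.8%, 9.1% and 9.4% at r = 0.3, 0.5 and 0.7. Simulated t-tests gave 8.7%–9.5%.

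**5. Chance baseline imbalance.** At SD 12 the baseline difference D between arms has SD 12·√(2/n), which is 3.8 mmHg at 20 per arm and 2.7 mmHg at 40. Given D, the attained comparison shifts by rD and the unadjusted change comparison by -(1-r)D:
- r = 0.3: 0.3D against -0.7D
- r = 0.5: 0.5D against -0.5D
- r = 0.7: 0.7D against -0.3D

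Neither unadjusted version removes the imbalance. Change is the more exposed of the two when r is below 0.5.

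**6. Effect of adjustment.** Let Y be the 6-month value, X the pre-procedure value and T the arm. The model Y - X = a + bT + cX is algebraically Y = a + bT + (c+1)X. The treatment estimate b and its test are identical, so once X is a covariate the choice between change and attained BP no longer affects the result. The model in 2.4 does not secure this, because it admits only covariates that differ significantly at baseline. Pre-procedure BP may not be among them.

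**The case against.** The strongest reply is that the wording is elliptical. Section 2.9.4.1 first names change as the primary variable, and 'Hence' derives the hypotheses from it. '(e.g.)' marks them as examples. Sections 1.1.1, 2.1 and 2.4 all say change, and the closing paragraph of 1.1.3 says the ambulatory analyses compare follow-up with the pre-procedure value. Attained 6-month BP is nowhere named as an outcome. This stands as the likelier reading. But primary hypotheses introduced as an example do not fix what is tested, and 2.9.1 does not settle it.

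A reader might infer more, and the documents do not support it:
- *That the t-test decides the trial.* Section 2.4 assigns a linear mixed model to the same endpoint and calls the analysis exploratory and descriptive.
- *That the two versions ask different questions.* Under 1:1 randomisation both estimate the same mean effect. They differ in precision and in their response to chance imbalance.
- *That the comparison of attained BP carries a baseline difference into the result in full, and that rewording to change cures this.* Step 5 shows a partial carry-over in both versions, and it is larger for change when r is below 0.5.
- *That the trial's false-positive rate is about 9%.* That figure needs both tests to be run and either to be claimed. The SAP does not offer that choice openly; its wording merely fails to exclude it.

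The disagreement rates also partly reflect low power in a small trial, and they rest on values that are not in the SAP.

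**Conclusion.** The inconsistency is real: the only formal H0 and H1 omit the change from pre-procedure that defines the primary endpoint. It matters because the named test is unadjusted. The two versions share one mean effect but yield different p-values. Under the stated assumptions they disagree on significance in about 24%–40% of trials. If either could be reported as the primary 5% test, the false-positive rate would be about 9% across r = 0.3–0.7. These are illustrations, since the SAP supplies none of the inputs. The exploratory status lowers the stakes, but both 2.4 and 2.9.4.1 keep a two-sided 5% level for the primary endpoint. A primary p-value is therefore to be expected, and its variable should be fixed. This is a wording error in operative text, to be corrected; it is not evidence that the trial intended to test attained BP.

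**What to change.** Amend 2.9.4.1 as follows:
- Define μ as the mean change in 24-h systolic ambulatory BP from one named pre-procedure value (P or B) to 6 months. H0: μ(RDN) - μ(sham) = 0. H1: μ(RDN) - μ(sham) ≠ 0.
- Delete 'significant' and '(e.g.)'.
- Name one primary analysis and use it in both 2.4 and 2.9.4.1. Preferably it includes the same pre-procedure value as a covariate whether or not it differs between arms. Change and attained BP then give the same treatment estimate, and chance imbalance in that value is handled.
- Label any unadjusted comparison of attained 6-month BP as descriptive, outside the 5% test.

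The cost is a few sentences and no new data. The sponsor must commit to P or B and to one model, and should do so without sight of unblinded results. Rewording the hypotheses alone would remove the contradiction but would leave the baseline reference, the choice of model and chance imbalance unsettled.

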2.9.4.2. Secondary efficacy variables

- 24-hour, daytime and nighttime ambulatory variables (Mobil-O-Graph):
 - o Mean systolic and diastolic 24-hour ambulatory BP
 - o Daytime mean systolic and diastolic ambulatory BP
 - o Nighttime mean systolic and diastolic ambulatory BP
 - o Mean 24-hour, daytime and nighttime heart rate
 - o Mean systolic and diastolic dipping, dipping type
 - o Mean 24-hour, daytime and nighttime pulse pressure
 - o Mean 24-hour, daytime and nighttime central systolic BP
 - o Mean 24-hour, daytime and nighttime central diastolic BP
 - o Mean 24-hour, daytime and nighttime augmentation index at 75 bpm
 - o Mean 24-hour, daytime and nighttime heart minute volume
 - o Mean 24-hour, daytime and nighttime peripheral resistance
 - o Mean 24-hour, daytime and nighttime reflexion coefficient
 - o Mean 24-hour, daytime and nighttime pulse wave velocity
 - o 24 hour central BP and pulse pressure
 - o Dipping status

- 24h hour , daytime and nighttime heart rate
- Office variables
 - Systolic and diastolic office BP
 - Pulse pressure
 - Heart rate
- Home BP (apnorm® Professional Touch)
 - Systolic and diastolic Home BP
 - Pulse pressure
 - Heart rate
- Antihypertensive Medication
 - medication number, drug burden index, antihypertensive load index
- Renal parameters
 - Serum creatinine, estimated glomerular filtration rate (eGFR)with serum creatinine (CKD-epi formula) and serum cystatin separately, eGFR derived from the combined creatinine/Cystatin-C formula
 - Proteinuria, albuminuria, urine sodium, urine potassium, urine creatinine (all parameters in mg/g creatinine)
- Safety endpoints and adverse effects
- Body composition parameters (BCM)
 - Weigth
 - Height
 - Body mass index
 - Overhydration (OH)
 - Overhydration in percent (OH%) of extracellular water (ECW)

2.9.5. Analysis of Safety and Tolerability

All safety analyses will be performed on the SAF population.

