1.1.5. Safety analysis

- Safety endpoints and adverse effects during 3, 6 and 12 months post-procedure compared between the 2 groups (RDN-Treatment group vs. Sham group).
- Listing of AE and ADE in original term provided for each patient (Solo-Population)
Listing of SAE, AESI, SADE in original term provided for each patient
Comparison of number / percentages of SAE, AE, AESI, escape rate between the 2 groups (RDN-Treatment group vs. Sham group)
- Increase of serum creatinine / eGFR (calculated based on CKD-epi) between visit 3a (week 0) and visit 3b, and visit 3a and visit 4 (week +3) between the 2 groups (RDN-Treatment group vs. Sham group) and in each group separately

Following events will be presented at all-time points post-procedure comparing 2 groups

All-cause mortality
New onset ESRD (eGFR<15 mL/min/m ² or need for renal replacement therapy)
Significant embolic event resulting in end-organ damage
Renal artery perforation or dissection requiring an invasive intervention
Major vascular complications requiring surgical repair, interventional procedure, thrombin injection, or blood transfusion
Hospitalization for hypertensive or hypotensive crisis
Hospitalization for major cardiovascular or hemodynamic related events
New onset stroke
New onset myocardial infarction
Suspicion of new onset renal artery stenosis by renal duplex ultrasound

Following AESIs will be presented as a table at all time points post-procedure comparing 2 groups

- All-cause mortality
- Hypertensive emergency resulting in hospitalization
- Hypotensive emergency resulting in hospitalization
- Hospitalization for heart failure
- Stroke, transient ischemic attack, cerebrovascular accident
- Acute myocardial infarction (STEMI/non-STEMI)
- Any coronary revascularization
- End stage renal disease, the need for permanent renal replacement therapy (i.e. the need for dialysis); doubling of plasma creatinine, eGFR <15ml/min/1.73m²
- Any renal artery complication requiring intervention (e.g. dissection; perforation)
- Major access site complications requiring intervention
- Significant embolic events resulting in end organ damage
- Procedure-related pain lasting for > 2 days
- Acute renal injury, defined as:

- Increase in serum/plasma creatinine to ≥ 1.5 times pre-procedure visit (week -1) or decrease of eGFR (derived from creatinine, CKD-epi) by 25% known to have occurred during 7 days post procedure or
- Urine volume < 0.5 ml/kg/h for 6 hours

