- Significant ($> 50\%$) and severe ($> 70\%$) new onset renal stenosis as diagnosed by renal angiogram or CTA/MRA
- Need for renal artery angioplasty or stenting

In addition, these AESIs will also be reported as 1-month post-procedure event rates:

- Any renal artery complication requiring intervention (e.g. dissection; perforation)
- Major access site complications requiring intervention
- Significant embolic events resulting in end organ damage
- Procedure-related pain lasting for > 2 days
- Acute renal injury, defined as:
 - increase in serum/plasma creatinine to ≥ 1.5 times pre-procedure visit (week -1) or decrease of eGFR (derived from creatinine, CKD-epi) by 25% known to have occurred during 7 days post procedure or,
 - Urine volume < 0.5 ml/kg/h for 6 hours

Following major combined safety endpoint (incidence of any major adverse events (MAE) through the FU) at all time points post-procedure comparing 2 groups

- All-cause mortality
- eGFR < 15 ml/min/1.73m² or permanent need for renal replacement therapy
- Hospitalization for hypertensive crisis defined by office (attended) BP $\geq 180/110$ mmHg with clinical symptoms
- Clinical manifestation of hypertension associated target organ damage requiring hospitalization
- New renal artery stenosis $> 75\%$ as assessed by computer tomography (CT)/magnetic resonance angiography (MRA) or diagnosed/confirmed by renal angiogram
- Individual components of the combined endpoint above

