1.3. Trial Flow Sheet

Enrollment of subjects occurred at the clinical sites only after the appropriate local study approvals, “Approval to Enroll” documentation from the Sponsor and written informed consent from subjects have been obtained.

Visit #	V1	V2	V3	V4	V5	V6	V7	V8 ⁷	V9	V10
Week	-4	-1	0	3	6	12	19	26	39	52
Informed consent	X									
Inclusion/exclusion criteria	X									
Medical history	X									
RDN/Sham Procedure			X							
Physical exam	X	X	X	X	X	X	X	X	X	X
24-h ABP measurement ¹	X	X				X		X		X
Office (attended) BP ²	X	X	X	X	X	X	X	X	X	X
Safety and efficacy lab	X	X	X	X	X	X	X	X	X	X
AEs/ADEs	X	X	X	X	X	X	X	X	X	X
UACR ³ , eGFR, Cystatin C	X	X				X		X		X
Urinary toxicological analyses ⁴		X				X		X		X
Body fluid composition		X						X		X
MRA of Renal Arteries ⁵		X								
Duplex ultrasound ⁶		X								X
Medication review	X	X	X	X	X	X	X	X	X	X

Visit schedule (# all visits can be scheduled +/-5days)

- 24-h ambulatory BP measurements will be conducted by mobilograph (IEM, Aachen) allowing also the assessment of central systolic BP in addition to brachial BP readings.
- Office (attended) BP according to ESH guidelines with automated oscillometric device while nurse/physician is in the room (attended visits).
- UACR – albumin/creatinine ratio.
- To assess adherence to prescribed medication
- MRA has only to be performed if no images (previous MRI, previous CT, previous angiogram) of anatomy of renal artery supply is available
- If the last duplex sonography examination displays signs of renal artery stenosis or is not fully evaluable according to the investigator’s discretion, an angiogram needs to be performed to rule out or diagnose any renal artery abnormality which can be compared with the angiogram performed at baseline.
- Patients who will not have 12 months follow up visit until June 2023 but thereafter will have a shorter follow up period of 6 months only and unblinding will take place after all data of the 6 months FU visit have been entered and secured in the database (the rationale is that the primary objective is change in blood pressure after 6 months!

2. Outcome Measures and Target Parameters

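### The consent-based safety set is the only denominator given for the renal artery stenosis outcomes; applied literally, it counts patients without post-procedure renal imaging as stenosis-free

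*SAP*

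**What the plan says.** **Population.** Section 2.9.5: "All safety analyses will be performed on the SAF population". Sections 2.3 and 2.4 define the SAF by informed consent alone. Section 2.9.1 asks for absolute and relative frequencies of categorical variables, with no rule for patients in whom an outcome was never assessed.

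**Outcomes (section 1.1.5).** Stenosis appears three times:
- in the event list: "Suspicion of new onset renal artery stenosis by renal duplex ultrasound";
- in the AESI list, at more than 50% and more than 70%: "new onset renal stenosis as diagnosed by renal angiogram or CTA/MRA";
- as a component of the combined MAE endpoint, at more than 75%: "as assessed by computer tomography (CT)/magnetic resonance angiography (MRA) or diagnosed/confirmed by renal angiogram".

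All three are to be compared between the arms at every post-procedure time point. For the second list the wording is "Following AESIs will be presented as a table at all time points post-procedure comparing 2 groups".

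**Imaging schedule (section 1.3).** Duplex is marked at weeks -1 and 52 only. MRA is marked at week -1 only, with the footnote "MRA has only to be performed if no images (previous MRI, previous CT, previous angiogram) of anatomy of renal artery supply is available". The follow-up angiogram depends on the duplex: it is required "If the last duplex sonography examination displays signs of renal artery stenosis or is not fully evaluable".

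**Length of follow-up.** Section 1.2 and the last flow-sheet footnote say that some patients were followed for six months only. No number is given.

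**Two places that do not fit.** Section 1.2 says that the baseline measurements were all repeated at weeks 12, 26 and 52. Section 2.9.3 says that enrolled patients who received neither RDN nor sham appear in listings and are not analysed further.

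**The concern.** A stenosis can be counted only in a patient whose renal arteries were examined. On the flow sheet, a patient whose follow-up ended at week 26 has no scheduled renal imaging after the procedure. The AESI and the MAE component are affected as well, because the scheduled duplex is their gateway to the confirmatory angiogram. With the SAF as the only denominator, such a patient enters the table as a non-case.

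New renal artery stenosis is a device risk, and section 2.4 limits the trial to exploratory and descriptive analysis. The absolute rates and their intervals are therefore what readers will use. A 12-month rate diluted by unimaged patients would look like reassurance that the data do not give. So would a zero at 3 or 6 months, where the flow sheet schedules no imaging.

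**Working it through.** **1. Is there a figure to reproduce?** No. The SAP states no stenosis rate, no size of the safety set and no number imaged. The check is of the text, followed by an illustration.

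**2. Who lacks scheduled imaging?** Recruitment stopped by 31.12.2022 (section 1.2). Patients whose 12-month visit would fall after June 2023 end at 6 months (section 1.3, last footnote). June 2023 minus 12 months is June 2022, so patients treated in roughly the last six months of recruitment are affected. Their number cannot be derived.

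**3. Dilution.** Let f be the share of an arm without post-procedure imaging. If off-schedule imaging finds no case:

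reported rate = rate among imaged × (1 − f)

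Both the 5% rate and f are assumed:

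| f | Reported rate |
|---|---|
| 10% | 5% × 0.90 = 4.5% |
| 25% | 5% × 0.75 = 3.75% |
| 50% | 5% × 0.50 = 2.5% |

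If f is equal in both arms, both rates shrink by the same factor. Their ratio is unchanged and their difference shrinks by (1 − f).

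**4. Precision.** Section 2.4 gives 20 randomised patients in the Bavarian cohort alone. Section 1.2 says that the target of 80 was missed, so at most 79 were randomised. At 1:1 this is 20/2 = 10 to 79/2 = about 39 per arm. With zero events, the exact two-sided 95% upper limit is 1 − 0.025^(1/n):

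| Counted in the arm | Imaged (assumed f) | Limit if all count | Limit if only imaged count |
|---|---|---|---|
| 39 | 35 (10%) | 9.0% | 10.0% |
| 39 | 29 (25%) | 9.0% | 11.9% |
| 10 | 9 (10%) | 30.8% | 33.6% |

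The imaged numbers are 39 × 0.90 = 35, 39 × 0.75 = 29 and 10 × 0.90 = 9.

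**5. Section 1.2 against the flow sheet.** Duplex is a week -1 measurement. If every baseline measurement was repeated at weeks 12, 26 and 52, duplex was due at all three visits. Patients ending at week 26 would then have had imaging at 3 and 6 months and would lack only the 12-month one. The flow sheet marks none of this before week 52. The same sentence would also repeat the MRA, which the flow sheet marks once. That suggests loose wording but does not settle the matter.

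**6. SAF against section 2.9.3.** Randomisation follows the angiogram (section 1.2), so consented patients who were never randomised have no arm. Section 2.4 describes the randomised subjects as all RDN or sham treated. Including or excluding the untreated therefore changes each arm's rate by 0. Only pooled figures could differ, and no screen-failure count is given from which to size that.

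**The case against.** **A denominator is fixed.** A reader might infer that the plan leaves the stenosis denominator open. It does not: section 2.9.5 names the SAF without exception. The defect is that the named set does not suit outcomes that depend on imaging.

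**Section 1.2 may supply the missing imaging.** This stands in part. If its sentence is meant literally, the gap at 3 and 6 months largely closes. The flow sheet is the more specific source and contradicts it, so the claim that week-26 patients were never scheduled for imaging rests on the flow sheet. Under either reading there is no rule for a duplex that was missed, could not be evaluated or fell after the end of follow-up.

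**Stenosis can be found off schedule.** True. The AESI and the MAE component are defined by angiogram, CT or MRA, and clinically prompted imaging before week 52 is possible. The formula in the working therefore assumes that no case is found that way. Mixing such imaging into the denominator would cause a different error, since patients imaged on suspicion are more likely to be cases.

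**The treatment comparison is hardly touched.** A reader might infer that the RDN-versus-sham contrast is biased. The SAP does not support that: allocation is 1:1, and the calendar rule for shorter follow-up does not depend on arm, so the shortfall should be roughly balanced.

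**The SAF conflict has little consequence.** This stands. A reader might infer that untreated patients dilute the per-arm safety rates, but they have no arm. The only total column that the SAP names is the one for demographics in section 2.9.3.

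**Conclusion.** The point holds in this form: the SAF is the only denominator for three outcomes that need renal imaging, no imaged-patient denominator is set, and the flow sheet leaves some patients without scheduled post-procedure imaging. Applied literally, the plan understates the absolute 12-month stenosis rate by the share not imaged and makes the intervals too narrow.

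The size is unknown. The 5% rate and the shares of 10% to 50% are assumptions, the arm size is known only to lie between about 10 and 39, and the dilution formula needs no case to be found off schedule. The contrast between arms should be little affected.

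Two matters go with it:
- Sections 1.2 and 1.3 disagree on when duplex was due and must be reconciled; the extent of the gap depends on the answer.
- The conflict between the consent-based SAF (sections 2.3, 2.4 and 2.9.5) and section 2.9.3 is real but minor.

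Other 12-month event rates have a related weakness. Section 2.8 runs AE observation to week 52 without allowing for patients who ended at week 26. Counted in the SAF, they would appear to have full 12-month follow-up.

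**What to change.** First reconcile sections 1.2 and 1.3 on duplex timing. Then set the following in the SAP:

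- **Duplex suspicion.** The denominator is patients with an evaluable scheduled follow-up duplex. A suspicious duplex counts as an event.
- **AESI (more than 50%, more than 70%) and MAE component (more than 75%).** The denominator is patients whose stenosis status is determined at the scheduled follow-up, either by an evaluable duplex without signs of stenosis or by CT/MRA or angiogram. A suspicious or non-evaluable duplex that CT/MRA or angiogram did not resolve is undetermined.
- **Accounting.** Give the numbers imaged, not imaged and undetermined per arm. List stenoses found by off-schedule imaging separately, with dates, outside the scheduled-imaging rate. At time points without scheduled imaging give counts only.
- **MAE and other events.** Show the MAE with and without the stenosis component. In other 12-month event rates, do not treat patients whose follow-up ended at week 26 as fully followed; Kaplan-Meier with censoring at last contact is one way.
- **Safety set.** Define the SAF in sections 2.3, 2.4 and 2.9.5 as randomised patients who received RDN or sham, analysed by treatment received. List the AEs of all other consented patients separately, which agrees with section 2.9.3.

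The cost is SAP wording, a few extra rows per arm, a second MAE line and one listing. Stenosis rates become slightly less favourable and their intervals wider, and they describe only patients who reached the scheduled imaging. Events in consented but untreated patients move to a listing, where they stay visible. No visit or procedure changes.
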